8.2 Safety and Tolerability Measures

8.2.1 Adverse Events

Adverse event (AE) assessments will be recorded on the Adverse Events eCRF. The term AE is used to include both serious and non-serious AEs.

Adverse events will be assumed to be treatment emergent unless (through comparison of full or partial dates) the onset date of the adverse event is specified as outside the treatment period or its exclusion from the treatment emergent period can be definitely ascertained from the end date or available month and year components of either of the start or end dates. An AE is also considered treatment emergent if the onset date is before the start of study treatment [Visit 2 /Day 1 + 1] but the severity worsened following that. If the AE onset date is missing or partial, the date will be compared as far as possible with the date of first dose of study treatment. Treatment emergent AEs (TEAEs) occurring during the study treatment period from the first dose of study drug medication up to and including 14 days after the end of treatment (i.e., not present at baseline or worsened in severity following start of treatment) will be reported as TEAEs.

For each AE, the following will be collected: the verbatim term for the AE, start date, end date or indication of ongoing, severity, indication of Serious AE, SAE criterion, relationship to study drug, action taken, and outcome. AEs will be coded using MedDRA version 20.0.

The onset day of the AE will be the difference between the date of onset of the AE and the date the study drug medication was first dispensed + 1. The duration of the AE will be the difference between the end date of the AE and its onset date + 1.

AE relationship to study drug can be classified by the investigator as definite, probable, possible, remote or unrelated. AEs severity can be rated as mild, moderate or severe.

AEs are classified as serious or non-serious. A serious adverse event (SAE) is any AE that is:

- Fatal
- Life-threatening
- Requires or prolongs hospital stay
- Results in persistent or significant disability or incapacity
- A congenital anomaly or birth defect
- An important medical event

Adverse events (including SAEs) are collected through the length of study for all enrolled subjects and for screen failures.

8.2.2 Other Safety Measures

Concomitant medications and concomitant procedures will be recorded on the Prior and Concomitant eCRF and Concomitant Procedures eCRF, respectively.

Concomitant AED administration since last visit will be recorded on the eCRF page.

Vital signs will be recorded on the Vital Signs eCRF. These data will include blood pressure, heart rate (supine for 5 minutes), temperature, respiratory rate, and weight.

Physical examinations will be recorded on the Physical Exam eCRF. These data will include Body System, normal/abnormal indication, and a description of the abnormality.

Routine 12-lead ECGs will be performed periodically during the study. Parameters including Heart rate, PR interval, QRS interval, RR interval, QT interval, and QTcF will be measured. These results will be recorded on the eCRF.

A brief neurologic evaluation examination will be made and recorded on the eCRF.

Clinical laboratory evaluations will be collected and returned electronically and not entered on an eCRF. Clinical Laboratory Evaluations will include the following:

- Hematology: hemoglobin, hematocrit, white blood count with differential, RBC count, platelet count, and calculated indices.
- Serum chemistry: blood urea nitrogen (BUN), calcium, chloride, creatinine, glucose, total bilirubin, direct bilirubin, alkaline phosphatase, aspartate transaminase (AST), alanine aminotransferase (ALT), total protein, albumin, globulin, sodium, potassium, phosphorus, and glucose. Serum creatinine will be used to calculate the creatinine clearance.
- Urinalysis: pH, specific gravity, protein, glucose, ketone, bilirubin, blood, nitrite, urobilinogen, and microscopic examination
- Pregnancy Tests – All females of child-bearing potential will undergo a serum pregnancy test for β -hCG (β -human chorionic gonadotropin).

All safety laboratory samples will be analyzed by a central laboratory.

The follow-up version of the Columbia Suicide Rating Scale (C-SSRS) will be assessed at Visit 2 and all subsequent visits throughout the study and entered on the eCRF.

8.3 Study Drug Exposure and Compliance

Information on subject drug compliance will be recorded on the study drug dispensing eCRF and the Study drug accountability eCRF. These data will include the dates and amount of drug dispensed and returned.

End of study data will be recorded on the End of Study eCRF. These data will include completion status, date of completion or discontinuation, primary reason for discontinuation, lost to follow-up information.

9 STUDY SUBJECTS

9.1 Determination of Sample Size and Randomization

No formal sample size estimation was involved for this long-term safety study. At least 20 subjects taking phenytoin and at least 20 subjects taking phenobarbital are planned to be enrolled. Additional subjects taking AEDs other than phenytoin or phenobarbital will be enrolled in order to expose at least 1,000 subjects for 6 months to further evaluate long term safety.

9.2 Analysis Populations

The following analysis populations (sets) will be defined:

Enrolled Population: All subjects who successfully meet their entry criteria and who have given informed consent to participate in this study will be considered enrolled subjects.

Safety Population: All subjects enrolled in the study who received at least one dose of study drug medication will be considered safety evaluable subjects.

For reporting purposes, three safety evaluable subgroups of subjects will be defined:

- Subjects taking phenytoin and YKP3089
- Subjects taking phenobarbital and YKP3089
- Subjects taking concomitant AEDs other than phenytoin or Phenobarbital and YKP3089

PK Population: All subjects enrolled in the study, who took at least one dose of study drug, and with at least one blood sample for PK.

All subjects who have given informed consent to participate in this study but failed one or more of the entry criteria will be considered screen failures.

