12.4 Safety Variable Analyses

All enrolled subjects who took at least one dose of study drug medication will be evaluable for safety. The number and percent of subjects reporting AEs (including treatment-emergent laboratory abnormalities) will be tabulated for all safety evaluable subjects and by the 3 subgroups of subjects defined in Section 12.2. All serious AEs (SAEs) will be tabulated separately as well as included with all reported AEs.

Physical and neurologic assessments, laboratory results, vital signs (including orthostatic measurements, weight and height), concomitant medications, ECGs, and C-SSRS will be summarized using descriptive statistics.

Extent of exposure and dose modifications will be tabulated.

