11.2 Protocol Deviations

Protocol deviations will be recorded by monitoring CRO (PPD) and recorded in their tracking system by deviation category. Protocol deviations will be included in a by-subject listing for subjects in safety population.

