11.4 Drug Exposure, Dosing, and Compliance

The extent of exposure to study drug (YKP3089 and concomitant AED) as recorded on eCRF will be provided in a listing by-subject and by visit.

Drug exposure will be summarized for exposure to YKP3089 (throughout the entire duration of the study for all 3 safety evaluable subgroups) and Phenytoin and Phenobarbital dosing during titration period (including only corresponding safety evaluable subgroups: subjects taking phenytoin and YKP3089, subjects taking phenobarbital and YKP3089, respectively).

The following parameters will be derived for each subject in the ~~ITT~~/safety population:

- Number of days/weeks/months YKP3089 study drug medication was taken

- Number of days on each YKP3089 dose level (12.5 mg up to an including 400 mg or maximum reported daily dose) during the titration phase, the maintenance phase and overall during study.
- Modal YKP3089 daily dose defined as the dose taken the most days during maintenance phase (Visit 9 to Visit 14); in case of ties (i.e., 2 different dose levels taken the same number of days), modal dose will be defined as the highest dose between the two.
- Daily phenytoin dose during titration phase (for subjects taking phenytoin and YKP3089 only)
- Daily phenobarbital dose during titration phase (for subjects taking phenobarbital and YKP3089 only)

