13 SAFETY ANALYSIS

Safety analyses will be performed using safety evaluable set. Separate by-subject AEs and SAEs listings will be prepared for screen failures.

Safety will be assessed by the frequency, severity of adverse events, as well as by clinical laboratory test values, 12-lead ECG recordings, vital sign measurements, physical and neurologic examinations, and the Columbia-Suicide Severity rating Scale (C-SSRS).

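### SAP 9.2 makes the Safety and PK Populations depend on meeting entry criteria, so a subject who was dosed but ineligible is, as written, a screen failure and left out of the safety tables

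*SAP*

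**What the plan says.** SAP 9.2 gives four linked definitions.

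- Enrolled: "All subjects who successfully meet their entry criteria and who have given informed consent to participate in this study will be considered enrolled subjects".
- Safety: "All subjects enrolled in the study who received at least one dose of study drug medication will be considered safety evaluable subjects".
- PK: "All subjects enrolled in the study, who took at least one dose of study drug", with at least one PK blood sample.
- Screen failure: a consented subject who "failed one or more of the entry criteria will be considered screen failures".

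Protocol 12.2 has the same enrolled and safety-evaluable definitions. Protocol 12.4 repeats the condition: "All enrolled subjects who took at least one dose of study drug medication will be evaluable for safety". On these populations, SAP 16 reports only that their names were revised.

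The Safety Population then governs the outputs. SAP 13 runs the safety analyses on it and adds: "Separate by-subject AEs and SAEs listings will be prepared for screen failures". SAP 11.4 introduces the derived exposure variables with "The following parameters will be derived for each subject in the" safety population. SAP 11.2 says: "Protocol deviations will be included in a by-subject listing for subjects in safety population".

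**The concern.** A safety population normally rests on exposure alone: whoever took the drug is counted. Here membership also requires eligibility, and the screen-failure definition takes in every consented subject who missed a criterion, dosed or not. A treated subject with an eligibility violation therefore falls on the wrong side of the line.

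This is a single-arm study meant to characterise long-term safety and to expose at least 1,000 subjects for at least 6 months. Adverse-event counts, subject-years and the number of subjects reaching 6 months could all omit people who took YKP3089. The deviation listing is limited to the same population, so the violation that removes a subject also removes that subject from the listing meant to show it.

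The omission need not be random. Exclusion criteria 1 to 3 (Protocol 7.4) concern previous drug hypersensitivity, previous drug rash and a first-degree relative with a serious cutaneous drug reaction. Protocol 4.5.1 gives three DRESS cases among 953 exposed subjects as part of the reason for the present design. A subject dosed in breach of one of those criteria bears directly on that question.

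**Working it through.** The plan states no figure to reproduce, because SAP 9.1 says there was no formal sample size estimation. The check is first one of logic and then one of size.

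**Logic.** Take consented subjects only and apply the SAP 9.2 definitions:

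- Enrolled = met criteria
- Safety = enrolled and dosed
- PK = enrolled and dosed and sampled
- Screen failure = failed a criterion

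| Met criteria | Dosed | PK sample | Enrolled | Safety | PK | Screen failure | Under the fix |
|---|---|---|---|---|---|---|---|
| yes | yes | yes | yes | yes | yes | no | unchanged |
| yes | yes | no | yes | yes | no | no | unchanged |
| yes | no | either | yes | no | no | no | unchanged |
| **no** | **yes** | **yes** | **no** | **no** | **no** | **yes** | Safety yes, PK yes, screen failure no |
| **no** | **yes** | **no** | **no** | **no** | **no** | **yes** | Safety yes, PK no, screen failure no |
| no | no | either | no | no | no | yes | unchanged |

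Only the two bold rows are wrong, and only they change under the fix.

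**Can those rows be populated?** Protocol 9.1.2 intends that only eligible subjects are dosed at Visit 2, so they should be uncommon. Error and late discovery remain possible, since several criteria rest on history. Protocol 7.3 also allows trivial exceptions to inclusion criteria with medical monitor approval, and the SAP does not say how those subjects are classified.

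**Size.** Let N be the number dosed, k the number removed, x the events among all N, and j the events among the k. The error in a reported proportion is |x/N − (x − j)/(N − k)|. It is largest when all events fall among those removed (x = j = k, giving k/N − 0 = k/N), or when everyone kept has the event and no one removed does (x = N − k, j = 0, giving 1 − (N − k)/N = k/N). The bound is therefore k/N. The documents give no k, so the values below are assumptions, with N = 1,000 as a round figure.

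| k removed | Denominator | Largest possible shift |
|---|---|---|
| 1 | 999 | 0.1 points |
| 5 | 995 | 0.5 points |
| 10 | 990 | 1.0 point |
| 20 | 980 | 2.0 points |

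The SAP also reports by subgroup. The phenytoin and phenobarbital groups are planned at 20 or more each. In a group of exactly 20, one removed subject could shift a percentage by up to 1/20 = 5 points.

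For a rare event, suppose the only case were among those removed. With k = 5 to 20 the tables would show 0 events (exact 95% upper limit 0.37% to 0.38%) instead of 1/1,000 = 0.10% (exact 95% CI 0.003% to 0.56%). The SAP plans no intervals. They are given here only to show the scale.

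**The case against.** The best reply is that enrolment and screen failure are statuses fixed at entry. Eligibility is confirmed at screening and again at Visit 2 before drug is dispensed. SAP 8.1 places enrolment at the signing of consent. SAP 11.1 puts screen-failure reasons in an enrolment status listing, and the exposure rules in SAP 11.4.1 provide only for enrolled subjects, as if every dosed subject were one. On that reading, a violation found later is a deviation and the subject stays in. A team might well work this way, but the explicit definition in SAP 9.2 says otherwise and nothing overrides it.

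Several other points stand and limit the impact:

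- The events are not hidden. SAP 8.2.1 collects adverse events for screen failures, and SAP 13 and 13.1 list them.
- Screen-failure reasons and demographics are listed (SAP 11.1 and 11.3). The by-subject exposure listing in SAP 11.4 states no population limit. Such a subject could therefore be traced, though not through the deviation listing.
- The PK part has little visible effect. The plasma-concentration summaries in SAP 12 do not name the PK Population, and the population PK analysis is reported separately.
- A subject admitted under an approved trivial exception can be argued to have been accepted as meeting the criteria.
- The 1,000 is the target for 6 months of exposure, not the number dosed. If more are dosed, k/N is smaller for the same k.

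These points argue for modest severity. They do not make the definition correct.

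**Conclusion.** The concern holds. Followed as written, SAP 9.2 leaves a dosed but ineligible subject out of the safety tables, the derived exposure and the deviation listing, and out of the PK Population. It is a stated rule that gives the wrong safety denominator, and it should be corrected.

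The effect is probably small. It depends entirely on an unknown k, and the overall bound of 0.1 to 2.0 points assumes k = 1 to 20 and N = 1,000. Any effect on rash or DRESS rates is possible but cannot be quantified from the documents. The conclusion rests on the literal reading; a team that fixes enrolment at Visit 2 might avoid the problem, but the SAP does not say it will.

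**What to change.** In SAP 9.2:

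- Define the Safety Population as all subjects who received at least one dose of YKP3089, regardless of eligibility.
- Define the PK Population as all subjects with at least one dose and at least one PK blood sample, without the enrolled condition.
- Limit screen failures to consented subjects who failed a criterion and were never dosed.

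In SAP 16, record this as a change from Protocol 12.2 and 12.4.

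Once this is done, a dosed but ineligible subject belongs to Safety but is neither enrolled nor a screen failure. The places that refer to enrolled subjects (adverse-event collection in SAP 8.2.1, the baseline listings in SAP 11.3, the exposure date rules in SAP 11.4.1) should be checked so that they also cover everyone dosed.

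The cost is three sentences in SAP 9.2, one entry in SAP 16 and that consistency check. No new data are needed. No protocol amendment is needed either, because SAP 4 says the SAP supersedes the protocol's statistical considerations and may be revised before database lock.

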10 STATISTICAL METHODS

10.1 General Methods

Summary statistics and analyses will be presented by overall (YKP3089) and by safety evaluable subgroups. Categorical variables will be summarized using counts and percentages. Descriptive statistics for continuous variables will include mean, standard deviation, median, minimum, and maximum values. No inferential analysis will be performed.

SAS® version 9.4 or later will be used for all statistical analyses.

10.2 Handling Missing Data

All summary results will be based on observed data, unless otherwise specified in the next sections. Data handling rules for missing or partial dates for concomitant and baseline AEDs and medication are included in [Appendix 2](#).

10.3 Visit Windows for Safety Analyses

The table below presents the visits assigned for safety analyses corresponding to the range of treatment study days (window) during which an actual visit (scheduled or unscheduled) may occur. Note that the windows defined for statistical analysis are different from the ones defined in Protocol Section 9.

Visit windows for laboratory tests, vital signs, and for Columbia Suicide Symptoms and Signs Rating Scale (CSSRS):

Derived Visit	Target Study Day [1]	Window [2]
Baseline (for laboratory tests and vitals)	Day 1	Days <= 1
Baseline (for C-SSRS)	Screening (Visit 1)	NA
Visit 2 (for C-SSRS)	Day 1	Days = 1
Visit 3	Day 15	>= Day 2 to <= Day 22
Visit 4	Day 29	>= Day 23 to <= Day 36

Visit 5	Day 43	>= Day 37 to <= Day 50
Visit 6	Day 57	>= Day 51 to <= Day 64
Visit 7	Day 71	>= Day 65 to <= Day 78
Visit 8	Day 85	>= Day 79 to <= Day 92
Visit 9	Day 99	>= Day 93 to <= Day 106
Visit 10	Day 113	>= Day 107 to <= Day 128
Visit 11	Day 143	>= Day 129 to <= Day 173
Visit 12	Day 203	>= Day 174 to <= Day 233
Visit 13	Day 263	>= Day 234 to <= Day 314
Visit 14	Day 365	>= Day 315 to <= Day 410
3 Months after 1 Year Treatment	Day 456	>= Day 411 to <= Day 501
6 Months after 1 Year Treatment	Day 547	>= Day 502 to <= Day 592
9 Months after 1 Year Treatment	Day 638	>= Day 593 to <= Day 684
12 Months after 1 Year Treatment	Day 730	>= Day 685 to <= Day 775
15 Months after 1 Year Treatment	Day 821	>= Day 776 to <= Day 866
18 Months after 1 Year Treatment	Day 912	>= Day 867 to <= Day 957
21 Months after 1 Year Treatment	Day 1003	>= Day 958 to <= Day 1049
24 Months after 1 Year Treatment	Day 1095	>= Day 1050 to <= Day 1112
Visit 15 (14-day follow-up)	Day of the last dose of study	>= day of the last dose of study drug+14

	drug+14 days	
Termination Visit [3]	Termination Visit during treatment period	

[1] Relative to the date of the first dose of study drug. For example, Day 1 = the date of the first dose of study drug.

[2] The study days evaluated for windows of visits during treatment period are on or prior to the last dose day.

[3] For subjects who decide not to continue in the study at any time (i.e., eCRF check box for “Continuing” is answered ‘No’), the Termination Visit is performed (as per Protocol Section 9.1.14). This is available for entry at any time as a separate visit on eCRF. The study day for the termination visit will be assigned relative to the first dose of study drug.

Visit windows for ECG measurements:

Derived Visit	Target Study Day [1]	Window [2]
Baseline	Day 1	Days <= 1
Visit 14	Day 365	>= Day 2 to <= Day 547
12 Months after 1 Year Treatment	Day 730	>= Day 548 to <= Day 914
24 Months after 1 Year Treatment	Day 1095	>= Day 915 to <= Day 1112
Visit 15 (14-day follow-up)	Day of the last dose of study drug+14 days	>= day of the last dose of study drug+14
Termination Visit [3]	Termination Visit during treatment period	

[1] Relative to the date of the first dose of study drug. For example, Day 1 = the date of the first dose of study drug.

[2] The study days evaluated for windows of visits during treatment period are on or prior to the last dose day.

[3] For subjects who decide not to continue in the study at any time (i.e., eCRF check box for “Continuing” is answered ‘No’), the Termination Visit

is performed (as per Protocol Section 9.1.14). This is available for entry at any time as a separate visit on eCRF. The study day for the termination visit will be assigned relative to the first dose of study drug.

Visit windows for Physical Exam measurements:

Derived Visit	Target Study Day [1]	Window [2]
Baseline	Day 1	Days <= 1
Visit 3	Day 15	>= Day 2 to <= Day 22
Visit 4	Day 29	>= Day 23 to <= Day 36
Visit 5	Day 43	>= Day 37 to <= Day 50
Visit 6	Day 57	>= Day 51 to <= Day 64
Visit 7	Day 71	>= Day 65 to <= Day 78
Visit 8	Day 85	>= Day 79 to <= Day 92
Visit 9	Day 99	>= Day 93 to <= Day 106
Visit 10	Day 113	>= Day 107 to <= Day 239
Visit 14	Day 365	>= Day 240 to <= Day 547
12 Months after 1 Year Treatment	Day 730	>= Day 548 to <= Day 914
24 Months after 1 Year Treatment	Day 1095	>= Day 915 to <= Day 1112
Visit 15 (14-day follow-up)	Day of the last dose of study drug+14 days	>= day of the last dose of study drug+14
Termination Visit [3]	Termination Visit during treatment period	

[1] Relative to the date of the first dose of study drug. For example, Day 1 = the date of the first dose of study drug.

[2] The study days evaluated for windows of visits during treatment period are on or prior to the last dose day.

[3] For subjects who decide not to continue in the study at any time (i.e., eCRF check box for “Continuing” is answered ‘No’), the Termination Visit is performed (as per Protocol Section 9.1.14). This is available for entry at any time as a separate visit on eCRF. The study day for the termination visit will be assigned relative to the first dose of study drug.

Visit Day is calculated by (Visit date – date of the first dose of study drug + 1).

The following conventions will be used for the derived visits with respect to safety variables:

1. If more than one actual visit date (including the unscheduled visits) falls within the same window, the visit closest to the target study day will be considered for analysis.
2. If 2 actual visit dates within a window are at the same distance from the target study day, the later visit with non-missing data will be considered for analysis. If repeated measurements are all taken on the same day, then the last measurement will be used.
3. Values recorded at Termination Visit will be mapped to the derived visit based on the window where the actual visit date falls in per rules 1 and 2 above.
4. Given the rules for completing the Termination Visit on eCRF (as defined in Protocol Section 9.1.14), the results recorded at Termination Visit will be summarized in the safety tables at both derived visit based on rule 3 above and at Termination Visit.

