1 PROTOCOL SYNOPSIS

Name of company	SK Life Science Inc
Title of study	An Open Label, Multicenter, Safety and Pharmacokinetic Study of YKP3089 as Adjunctive Therapy in Subjects with Partial Onset Seizures
Protocol number	YKP3089C021
Phase of development	Phase 3
Study duration	After 12 months of participation in the study, subjects will be evaluated for treatment response. Those who are benefiting from treatment with YKP3089 may continue use of the drug at the discretion of the investigator, until development is stopped by SK Life Science Inc or the product is approved for marketing, or anytime at the discretion of SK Life Science Inc.
Indication	Partial-onset epilepsy
Study center(s)	Approximately 80-110 sites (multiple countries)
Number of subjects	At least 20 subjects taking phenytoin and at least 20 subjects taking phenobarbital. Additional subjects taking AEDs other than phenytoin or phenobarbital, will be enrolled in order to expose a total of at least 1,000 subjects for at least 6 months.
Objectives	
The objective is to evaluate the safety and pharmacokinetics of YKP3089 and concomitant AEDs when administered as adjunctive therapy for the treatment of partial seizures. The evaluations will include:
 
 1. Phenytoin-YKP3089 interaction 2. Phenobarbital-YKP3089 interaction 3. Long term safety of YKP3089 as adjunctive therapy in partial onset seizures 4. Population pharmacokinetics of YKP3089 and concomitant AEDs.
Inclusion and exclusion criteria	
Subjects to be enrolled in the study include:
 
 1. Subjects on stable doses of phenytoin 2. Subjects on stable doses of phenobarbital 3. Subjects on stable doses of other concomitant AEDs 
Subjects who meet all inclusion and no exclusion criteria listed in Section 7.3 and Section 7.4 of the protocol are eligible to enroll.

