Visit 15 represents the Follow-up Visit after discontinuation of study drug. This final visit will take place 14 days after the subject's last dose of YKP3089—at any time during the open-label treatment or after 12 months of open-label treatment if there is no additional treatment beyond that point.

As shown in [Table 1](#), the following assessments will be performed at Visit 15:

- Record vital signs
- Measure weight
- Conduct full neurologic examination
- Administer C-SSRS (Since Last Visit version)
- Serum pregnancy test (for female subjects of child-bearing potential)
- Draw blood for laboratory safety assessment
- Record concomitant medications
- Perform drug accountability if tapered
- Record AEs

No study drug will be dispensed.

9.1.16 *Open-Label Extension Beyond Year One*

Subjects who complete Visit 14 and will continue in the open-label treatment beyond year one will adhere to the following visit schedule. The investigator will schedule a return visit in 3 months. Subjects will have study visits every 3 months for a total of 4 visits per study year. The investigator will perform some or all of the following assessments depending up on the visits.

Perform the following every 3 months from Visit 14

- Record vital signs
- Conduct brief neurologic examination if required
- Administer C-SSRS (Since Last Visit version)
- Perform urine pregnancy test (for female subjects of childbearing potential)

- Record concomitant medications
- Perform drug accountability
- Record AEs
- Dispense open-label study drug bottles as instructed by IWRS

Perform the following every 6 months from Visit 14

- Measure weight
- Draw blood for laboratory safety assessment

Perform the following every 12 months from Visit 14

- Perform full physical exam
- Perform 12-lead ECG once
- Obtain urine for urinalysis

This pattern will continue at the discretion of the investigator until development is stopped by SK Life Science Inc, the product is approved for marketing, or anytime at the discretion of SK Life Science Inc.

After the first year of open-label treatment, the visits will be numbered sequentially beginning with Visit 16.

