8 STUDY PROCEDURES AND ASSESSMENTS

The study will include multiple study visits during the 3 years duration. Titration phase will include 7 study visits (Visit 2 to Visit 8), Maintenance phase will include up to 5 visits (Visit 9 to Visit 14). Visit 15 is considered 14-days after last dose follow-up visit. Subjects who benefit from treatment, may continue in an Open-Label Extension beyond year one with visits occurring every 3 months.

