11.4.1 Exposure to YKP3089 study drug

The following will be summarized overall and by safety evaluable subgroups:

- Length of exposure (weeks and months)
- Number and percentages of subjects by time intervals (0-<1 weeks, 1-<2 weeks, 2-<4 weeks, 4 - <12 weeks, 12 - <24 weeks, 24-<48 weeks, 48-<96 weeks, >=96 weeks)
- Number and percentage of subjects by exposure categories: >= 1 dose, >=6 months, >=12 months, >=18 months, >=24 months, >=36 months

For any interim reporting of the results from this study, only applicable exposure categories based on maximum duration of exposure observed will be included in the summary tables).

Derivation for length of exposure to YKP3089:

- Length of exposure to YKP3089 (days) = (stop date – start date + 1).
- Length of exposure to YKP3089 (weeks) = length of exposure to YKP3089 (days)/7
- Length of exposure to YKP3089 (months) = length of exposure to YKP3089 (days)/30.4

Start and stop dates are define as per rules below:

Analysis Period	Subject Participation	
	Enrolled and discontinued study	Enrolled and ongoing at date of data cut-off
Overall	Start Date = First dose date Stop Date = last dose date	Start date = First dose date Stop Date = date of data cut-off
Titration Phase	Start date = First dose date Stop Date = Visit 9 date OR Last dose date	Start date = First dose date Stop Date = Visit 9 date OR date of data cut-off
Maintenance Phase	Start Date = Visit 9 date + 1 Stop Date = Last dose date	Start Date = Visit 9 date + 1 Stop Date = date of data cut-off

Descriptive statistics (mean, standard deviation, median, minimum, and maximum) will be provided to summarize the length of exposure (in weeks and in months) for each safety evaluable subgroup and overall. Similar summary results will be prepared by modal dose within each safety evaluable subgroup.

The number and percentage of subjects at each dose level will be summarized by safety evaluable subgroup and overall for the titration phase, the maintenance phase and overall during study. The length of exposure to YKP3089 at each dose level (from 12.5 mg up to maximum daily dose reported in study) will be summarized using descriptive statistics (mean, standard deviation, median, minimum, and maximum).

Dosing duration will also be expressed in terms of total subject years of exposure to YKP3089, calculated as the sum of all subject exposure days, divided by 365.25.

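### SAP 10.3 ends the last on-treatment visit window at Day 1112 although treatment has no end date, so later routine assessments have no derived visit; ECG loses most

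*SAP*

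**What the plan says.** SAP 10.3 has three window tables, and all three end on-treatment windows on the same day. For labs, vital signs and C-SSRS the last window, with target Day 1095, is ">= Day 1050 to <= Day 1112". For ECG and for physical exam it is ">= Day 915 to <= Day 1112". Only the Visit 15 row, tied to the last dose, and the Termination Visit row come after it. There is no open-ended row and no rule for on-treatment values beyond the last window. SAP 15.1 displays summary tables by these derived visits, and SAP 10.4 computes change from baseline from them.

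The protocol sets no last visit. The synopsis lets subjects who benefit continue "until development is stopped by SK Life Science Inc or the product is approved for marketing", or until the sponsor decides otherwise. Protocol 9.1.16 states "Subjects will have study visits every 3 months for a total of 4 visits per study year" and then "This pattern will continue at the discretion of the investigator until development is stopped by SK Life Science Inc". SAP 11.1 repeats the open-ended rule, and the exposure categories in SAP 11.4.1 run to ">=12 months, >=18 months, >=24 months, >=36 months" with no upper limit.

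SAP 8, however, says "The study will include multiple study visits during the 3 years duration". SAP 4 promises that substantial differences from the protocol are identified, but SAP 16 does not list a three-year limit among the changes.

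**The concern.** Long-term safety is a stated objective of the study. Subjects treated beyond about three years carry the longest exposure, and they are the ones whose routine visits run past the last window. Followed as written, the SAP counts them in its top exposure category but has no row for their later routine measurements in the by-visit tables. The Day 1112 limit also has no stated basis and does not follow the pattern of the other windows.

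**Working it through.** **Inputs.** Targets and bounds come from the three tables in SAP 10.3. Protocol 9.1.16 gives the schedule after Visit 14: vital signs and C-SSRS every 3 months, labs and weight every 6 months, ECG and full physical exam every 12 months. Protocol 9 allows ±7 days at these visits. SAP 11.4.1 converts 30.4 days to a month.

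**Step 1: the rule behind the windows.** Each upper bound is close to the midpoint between its target and the next.
- Labs table, 9 months after year 1: (638 + 730)/2 = 684; stated 684.
- Labs table, 21 months after year 1: (1003 + 1095)/2 = 1049; stated 1049.
- ECG and physical exam, 12 months after year 1: (730 + 1095)/2 = 912.5; stated 914.

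All other upper bounds agree with this rule within 2 days.

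**Step 2: the last bound.** The same rule does not give 1112.
- Labs table: the next target is about 1095 + 91 = 1186, so the midpoint is (1095 + 1186)/2 = 1140.5.
- ECG and physical exam: the next target is about 1095 + 365 = 1460, so the midpoint is (1095 + 1460)/2 = 1277.5.
- Stated in all three tables: 1112 = 1095 + 17.

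| Window (time after year 1) | Days before target | Days after target |
|---|---|---|
| Labs table, 3 to 21 months | 45 | 45–46 |
| Labs table, 24 months | 45 | 17 |
| ECG and physical exam, 12 months | 182 | 184 |
| ECG and physical exam, 24 months | 180 | 17 |

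An ECG taken 180 days before Day 1095 is kept; one taken 18 days after it is not.

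**Step 3: which visits fall outside.** A Day 1095 visit within the protocol's ±7 days (Days 1088 to 1102) is captured. The next 3-monthly visits, at about 1095 + 91k = 1186, 1277, 1368 and 1459, match no window in any table, and neither does any later one.

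**Step 4: a subject still on drug at four years (illustration).**
- Vital signs and C-SSRS: 3 years × 4 = 12 extension visits; 8 have a window and 4 do not (33%).
- Labs: 3 × 2 = 6; the last 2 have no window.
- ECG and full physical exam: 3 × 1 = 3; the last has no window.

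If the subject instead stops at four years, that visit becomes the Termination Visit with its own row. The losses fall to 3 of 12, 1 of 6 and 0 of 3.

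**Step 5: comparison with the exposure table.** The 36-month category begins at 36 × 30.4 = 1094.4 days. Day 1112 is 1112/30.4 = 36.6 months, so the windows stop about half a month into a category with no upper limit.

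**Step 6: where later routine values still appear.**
- Labs (SAP 13.2): overall shift tables and liver-test categories at any time after baseline. The by-visit means, changes and shifts lose them.
- Vital signs (SAP 13.4): the threshold criteria use any post-baseline value. The by-visit summaries lose them.
- C-SSRS (SAP 13.6): the shift to any post-baseline visit. The by-visit results lose them.
- Physical exam (SAP 13.5): the by-timepoint tabulation and shift lose them. The further shift to follow-up does not define follow-up.
- ECG (SAP 13.3): the value and change summaries, the QTcF and heart-rate threshold counts and the interpretation shift are all per timepoint. No any-time table exists, so only listings remain.

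**The case against.** A reader might infer that all data after Day 1112 vanish from the safety tables. The documents do not support that. The Termination Visit row has no day limit, and Protocol 9.1.14 and 9.1.16 put vital signs, labs, C-SSRS, ECG and full physical exam at that visit. The Visit 15 row is tied to the last dose. The any-time summaries in Step 6 and the by-subject listings do not depend on the windows, and neither do the adverse-event and exposure tables. Much of the long-term safety information is therefore kept.

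It can also be said that ending at three years follows SAP 8, that the 36-month exposure category is no contradiction in itself because the Day 1095 visit has a window, and that by-visit rows far into the extension may hold few subjects. The study is descriptive (SAP 10.1), so no test is affected. SAP 14 allows an early data cut-off, and SAP 4 allows revision before database lock.

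These points limit the loss but do not remove it. The three-year statement conflicts with the protocol's open-ended treatment and with SAP 11.1, and it is not a declared change. None of the retained summaries gives routine late ECGs a table. The Termination Visit rules also fail after Day 1112: conventions 3 and 4 of SAP 10.3 require those results to appear at a derived visit as well as in the Termination row, and there is no derived visit to map them to.

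**Conclusion.** The point holds for routine on-treatment assessments after Day 1112. They have no derived visit and leave the by-visit summary, change-from-baseline and shift tables, with no rule to cover them. ECG is the sharpest case: a routine QTcF above 500 msec after Day 1112 would be counted in no table and seen only in listings.

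The size depends on how many subjects are still on drug beyond Day 1112 at data cut-off. The documents do not give this; it may be none at an early cut-off, and it grows as the extension continues. The four-year figures (4 of 12, 2 of 6, and 1 of 3 for ECG and physical exam) assume a subject still on drug at four years with visits on schedule. The projected visit days assume 91-day spacing. No inferential result is affected.

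**What to change.** 1. Continue the midpoint pattern to last dose or data cut-off, with targets about every 91 days for labs, vital signs and C-SSRS and about every 365 days for ECG and physical exam. The window at target Day 1095 would then end near Day 1140 in the labs table and near Day 1277 in the other two. Extended windows also make the Termination Visit mapping workable.
2. If sparse rows are a worry, use one open-ended last window instead, with its own selection rule such as the last on-treatment value. Simply removing the upper limit from the Day 1095 window is not enough: convention 1 of SAP 10.3 picks the value closest to target, so a subject seen near Day 1095 would still lose every later value.
3. Add an any-time post-baseline row, using scheduled and unscheduled ECGs, to the QTcF and heart-rate threshold tables in SAP 13.3.
4. Reconcile the three-year statement in SAP 8 with the open-ended protocol. If by-visit reporting is meant to stop at three years, say so in SAP 16 and state how later data are reported.

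The cost is a few table rows or one general rule, minor programming, and some rows with few subjects. No new data are needed.
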